Protocol

Objective. The primary objective of the current IRB application is to define the time course of change in pain score after 5 min heating of the skin applied at intervals during and following infusion of intravenous oxytocin in order to create a PK/PD model for oxytocin-induced analgesia. The proposed study design will advance the preliminary data by use of a dosing regimen predicted to produce the maximum achievable effect with oxytocin in a manner that will validate and more precisely describe PK/PD model from preliminary data.

A secondary objective is to test for effects of subject sex or age on oxytocin effect.

Overview. Equal numbers of adult men and women, age 18-75 will be recruited. Subjects will report to the Pain Clinical Research Unit (CRU) or the CTSI CRU for four visits, the first to confirm consent and train the individuals in all heat pain procedures, the second to infuse oxytocin intravenously, record heat pain ratings at 15 min intervals for 2 hr, then once more at 3 hr, and the third and fourth to record heat pain ratings approximately 24 hr and 5-7 days after oxytocin infusion. A PK/PD model will be generated from these PD measures (heat pain ratings). We will not withdraw blood and measure oxytocin for PK in these subjects nor in subsequent studies to be submitted to the IRB. Rather, we will use the population PK model of intravenous oxytocin established from a past study of 11 volunteers and an ongoing study in 24 other volunteers.

[figure not shown]

Figure 1. **A)** plasma oxytocin concentrations with LC/MS (red/black lines) compared to plasma by RIA (blue lines. **B)** modeled plasma oxytocin concentrations (blue line) and observed (circles) and modeled (green dash) pain scores after 10 min infusion of 17 μ g oxytocin. **C)** as in B) but after 30 min infusion of 14 μ g oxytocin

Phase II trials

Setting

The training visit will occur at either the Pain CRU at Piedmont Plaza 2 or the CTSI CRU. Drug study visits will occur on the main campus at CTSI CRU.

Subjects selection criteria

The study will enroll healthy subjects.

Inclusion Criteria

1. Male or female ≥ 18 and < 75 years of age, Body Mass Index (BMI) <40 .
2. Generally in good health as determined by the Principal Investigator based on prior medical history, and as assessed to be American Society of Anesthesiologists physical status 1, 2

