The projected sample size is 24 evaluable subjects with complete data sets. We request to enroll up to 26 subjects. Our current estimates indicate that the confidence interval for studies of 21 individuals with pain intensity ratings in two preliminary studies will determine the pharmacodynamic parameters with a corrected confidence range < 20%. A corrected confidence range < 20% implies that mixed effect analysis will distinguish covariate effects in the range of 40% in a study with 21 or more subjects. This is the range at which the covariate effect may be clinically consequential. In practice, mixed-effects analysis with NONMEM is often sensitive to covariate effects smaller than predicted by preliminary analyses. The sample size is increased to 24 to provide covariate assessment for age, weight, and sex.

Interventions and Interactions

At all study visits participants will be queried regarding recent history of symptoms commonly associated with COVID-19 or recent close contacts with anyone with a positive COVID-19 test.

Study Visit 1:

The participant will report to the Pain CRU or the Wake Forest CTSI CRU. The participant will review and sign the Informed Consent. After informed consent is adequately obtained, a detailed medical history will be obtained from the participant, female participants will have a urine pregnancy test performed to determine pregnancy status. Vital signs to include blood pressure (BP), heart rate (HR), respiratory rate (Resp) and oxyhemoglobin saturation by pulse oximetry (POX) will be measured and recorded along with height and weight.

Once eligibility has been determined the participant will be trained in study procedures. This will include pain ratings to brief (5 sec) heat stimuli on the lateral calf to 39, 41, 43, 45, 47, and 49°C and then a pain intensity rating each minute for 5 mins during heating to 45°C. If the pain report to 45°C is ≤ 2 at the end of the 5 min, a second trial using 46°C will be done. If the 46°C results in pain intensity ≤ 2, a third trial with 47°C will be performed, and if that trial results in pain intensity ≤ 2, a third trial with 48°C will be performed. Subjects who have pain intensity ≤ 2 with the 48°C 5-min stimulus will not be further studied. The duration for visit 2 will be approximately 2 hours.

Study Visit 2

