The primary analysis will use NONMEM to create a PK/PD model of oxytocin on average pain ratings each min for 5 min during the noxious heat stimulus. To do so, pain scores over time will first be modeled using NONMEM with derived parameters of maximum effect (Emax), predicted concentrations from the PK/PD model to produce a 50% and 90% maximum drug effect (C50 and C90, respectively), the steepness of the dose response curve (γ), and the time to peak effect. Inter-subject variability (e.g., biological variability) will evaluate additive, proportional, and exponential models. Residual intrasubject variability (e.g., noise) will typically require an additive and multiplicative error model. The influence of covariates (e.g., age, sex, weight) on model parameters will be analyzed by serial inclusion / exclusion, with significance determined by the likelihood ratio test ($p < 0.01$ if the decrease in -2 log likelihood exceeds 6.6 ($\chi^2_{0.99}$, $df = 1$)). Parameters will be estimated using first-order conditional estimate with η - ε interaction.

Covariate effects deemed significant by likelihood ratio test will be validated using jackknife cross-validation [10]. Jackknife cross-validation provides an estimate of the utility of the covariate to inform the pharmacodynamics in a future individual, rather than merely characterize the pharmacodynamics in the individuals from which the model was derived. The jackknife cross-validation divides the data into N subsets. Each subset leaves out a single individual. The parameters of the model are re-estimated for each subset with and without the covariate being validated. The inaccuracy (mean $((|measured - predicted|) / predicted)$), of the model with and without the covariate is measured in the excluded individual. The covariate is only being included in the final model if the improvement in model accuracy in the N iterations is significantly greater than 0. Jackknife cross-validation helps compensate for NONMEM's ability to identify very small covariate effects that do not meaningfully contribute to accuracy in future patients.

Expected outcomes. Based on pain ratings and an estimate of the PK/PD model from preliminary data (Fig 1), we anticipate that the maximum oxytocin effect is a 50-60% reduction in pain rating from the 5 min heat stimulus.

Human Subjects Protection

Subject Recruitment Methods

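### The sex/age objective is answered only by a rule for keeping covariates in a predictive model, and a dropped covariate does not by itself exclude the roughly 40% effect the plan treats as possibly consequential

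*Combined protocol and SAP*

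**What the plan says.** The Objective section states: "A secondary objective is to test for effects of subject sex or age on oxytocin effect". It names no pharmacodynamic parameter and no scale.

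Sample Size starts from two preliminary studies totalling 21 people, said to give pharmacodynamic parameters with a corrected confidence range below 20%. It infers that "mixed effect analysis will distinguish covariate effects in the range of 40% in a study with 21 or more subjects", and adds: "This is the range at which the covariate effect may be clinically consequential". It then says: "The sample size is increased to 24 to provide covariate assessment for age, weight, and sex". The corrected confidence range is not defined, and no confidence level or power is given.

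The Analytical Plan lists Emax, C50, C90, γ and time to peak effect. The influence of covariates "on model parameters will be analyzed by serial inclusion / exclusion", with "significance determined by the likelihood ratio test" at p<0.01 (a drop of more than 6.6 in -2 log likelihood). Covariates that pass go to a leave-one-subject-out jackknife: "The covariate is only being included in the final model if the improvement in model accuracy" is significantly above zero. No significance level is stated for this second test. Nothing is said about reporting the estimate for a covariate that is dropped, or about how its absence should be read.

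**The concern.** Two questions share one procedure. The secondary objective asks whether sex or age changes the effect of oxytocin. The retention rule asks which covariates belong in a model meant to predict new individuals. The jackknife suits the second question, and the plan says openly that it is there to remove effects that do not improve prediction. It is not a test of whether an effect exists, nor a measure of its size. A sex effect could be significant at p<0.01, fail the jackknife, and leave the final model with no stated estimate.

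If the only result is that a covariate was not retained, a reader cannot tell whether a 40% effect has been ruled out or is still open. That matters because covariate assessment is the stated reason for going from 21 to 24 subjects. For scale, the plan says: "we anticipate that the maximum oxytocin effect is a 50-60% reduction in pain rating". If the 40% is taken as a relative difference in Emax, which the plan does not say, it equals 0.40 × 50 to 0.40 × 60, or 20 to 24 percentage points of pain reduction.

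**Working it through.** **Inputs.** The 20% bound at n=21, the 40% effect and 24 evaluable subjects come from Sample Size. Equal numbers of men and women come from Overview, giving 12 v 12. The p<0.01 cut-off comes from the Analytical Plan. The 0.99 quantile of chi-square with 1 df is 6.635, which agrees with the stated 6.6.

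**Assumptions.** 95% level; normal approximation; effects relative to the parameter mean; the same information per subject as in the preliminary studies; 20% used as the value although the text gives it as an upper bound. This is a two-group stand-in for sex, not a NONMEM run. Age is not computed, because no age contrast is specified.

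**The plan's own 40%.** If 20% is a 95% half-width at n=21, SE = 0.20/1.96 = 0.102. With an equal split, the difference has twice that SE, 0.204, and a half-width of 1.96 × 0.204 = 0.40. So this reading reproduces the step from 20% to 40%. A true effect equal to the half-width has 50% power at two-sided 0.05, and 27% at the plan's 0.01.

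**At n=24.** SE(24) = SE(21) × √(21/24), and SEdiff = 2 × SE(24).

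| Quantity | 20% is a full 95% width | 20% is a 95% half-width | 20% is an SE |
|---|---|---|---|
| SE(21) | 0.051 | 0.102 | 0.200 |
| SEdiff | 0.0955 | 0.191 | 0.374 |
| Largest estimate missing p<0.01: 2.576 × SEdiff | 25% | 49% | 96% |
| Its upper 95% limit: 4.536 × SEdiff | 43% | 87% | 170% |
| Largest estimate whose interval excludes 40%: 0.40 − 1.96 × SEdiff | 21% | 3% | none |
| Interval half-width: 1.96 × SEdiff | ±19% | ±37% | ±73% |
| Power at the likelihood ratio step for a 40% effect: Φ(0.40/SEdiff − 2.576) | 95% | 31% | 7% |

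Failing the likelihood ratio test excludes 40% by itself only if 4.536 × SEdiff < 0.40. That means SEdiff < 0.0882, or a half-width at n=21 below 1.96 × (0.0882/2) × √(24/21) = 9.2%.

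**The jackknife step.** With the same SE, any estimate that passes the likelihood ratio test exceeds the threshold in the table. Its upper limit is therefore above 43% even in the first column. If the jackknife then drops it, the covariate is not retained although its interval reaches past 40%.

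To see whether this is only theoretical, a linear simulation used 12 v 12, a true 40% sex effect, and an assumed one-sided 0.05 test of the jackknife gain. On the full-width reading, 93% of trials pass the likelihood ratio test, but only about 33% to 49% also pass the jackknife, depending on how prediction error is scaled. On the half-width reading, 32% pass the first step and about 1% to 7% pass both. These figures show the direction of the problem. They do not forecast NONMEM results.

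**The case against.** **The estimates will exist anyway.** A likelihood ratio test requires fitting the model with the covariate, the jackknife refits it with and without, and a retained covariate has a coefficient in the final model. This stands. The gap is a reporting and interpretation rule for dropped covariates, not a missing analysis.

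**The objective is worded as a test, and a test is supplied.** This is true of the likelihood ratio step. The jackknife, however, has the last word on retention and tests something else. A reader might also infer that the sponsor intends to report non-retention as no effect. The documents do not say so; they leave the interpretation open.

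**On the favourable reading the likelihood ratio step is informative.** With 20% as a full width, the test fails while 40% stays open only if the estimate lies between 21.3% and 24.6%. That happens in about 1.6% of trials with no sex effect and 2.8% with a true 40% effect. This stands for the first step, but it does not cover covariates removed at the second.

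**The new study may be more precise.** It uses two infusions and staggered testing times, and the 20% is an upper bound. This is also fair, and it is why the figures above are only illustrations.

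**Choosing one parameter is a preference.** The plan lists several, and Emax above is only an example. The choice belongs to the sponsor, but the 40% has no definite meaning until one is made.

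**Conclusion.** The point holds as a gap in the Analytical Plan. The secondary objective is answered only by a retention rule whose final step measures predictive gain, and non-retention alone does not exclude an effect of about 40%. This follows from the text, and holds for sex on each reading tabulated.

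How often it would mislead cannot be fixed from the documents. For sex, power at the likelihood ratio step for a 40% effect runs from 7% to 95% across the readings of the undefined 20%, and a half-width below about 9.2% would make failure of that test sufficient to exclude 40%. Nothing has been computed for age.

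A reader might infer from the lower power figures that 24 subjects are too few. The documents do not support that: on the full-width reading, power at the first step is about 95%. This is a worthwhile, inexpensive improvement, not a fault in the sample size.

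**What to change.** Keep the likelihood ratio test and the jackknife unchanged for choosing the predictive final model. For the secondary objective, add to the Analytical Plan:

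> The effects of sex and of age (per a prespecified contrast, for example per decade) on one pharmacodynamic parameter prespecified by the sponsor will be estimated in one prespecified model. They will be reported with 95% intervals and the likelihood ratio p-value, whether or not the covariate is retained. The intervals will be read against 40%. Non-retention alone will not be reported as no effect.

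Weight can stay under the existing rule, since the secondary objective names only sex and age.

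In Sample Size, define the corrected confidence range (confidence level, and whether it is a full width, half-width or standard error). From the sponsor's own preliminary standard errors, state the effect detectable at p<0.01 with 24 subjects, saying that it covers the likelihood ratio step only.

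The cost is a few sentences and one extra NONMEM run, with no additional subjects. The downside is that the intervals may be wide (for sex, about ±19% or ±37% on the full-width and half-width readings), and the stated sensitivity may turn out less favourable than 40%.

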On the second visit, the participant will report to the CTSI CRU. Baseline vital signs (BP, HR, Resp, POX) will be obtained for a baseline measurement, a catheter inserted into a peripheral vein in the upper extremity and pain report to 5 min heating of skin on the calf at the temperature determined in Visit 1 will be recorded. Subjects will then receive two 30 min infusion of oxytocin, 17 µg (provided by the research pharmacy), with infusions separated by 30 min. Pain ratings to 5 min heat pain testing will be performed at 15 min intervals for 2 hr, then at 3 hr after initiation of the first infusion. The first 5 min heat stimulus will end at 15 min after beginning the first oxytocin infusion in the first 8 subjects. In the event that there is no effect of oxytocin on heat pain, we will stop recruitment and assess whether protocol amendment or termination will be requested. If there is an effect, the remaining 16 subjects will be randomized to have the first 5 min heat stimulus end at 10 or 20 min after the first oxytocin infusion begins. In this fashion there will be 3 cohorts of 8 subjects each, thereby providing pain rating measurements in 8 subjects every 5 min after the first 5 minutes of the infusion. The duration for study visit 2 will be approximately 4 hours.

Study Visit 3

On the third visit, the participant will report to the CRU approximately 24 hr after the beginning of the infusion (acceptable range 20-28 hr) and heat pain ratings acquired on 3 trials separated by 10 min. The duration for study visit 3 will be approximately 1 hour.

Study Visit 4

On the fourth visit, the participant will report to the CRU 5-7 days after the day of oxytocin infusion and heat pain ratings acquired on 3 trials separated by 10 min. The duration for study visit 4 will be approximately 1 hour.

Safety and Monitoring:

Assessment of Side Effects: Peripheral oxyhemoglobin saturation, BP and HR will be measured non-invasively before and 5, 10, 30, 60, 90 and 120 minutes after oxytocin infusion. Subjects will be informed to report any subjective sensations during or after oxytocin administration and will be queried at the same intervals as vital sign monitoring for any subjective sensations.

Treatment of Side Effects: Significant cardiorespiratory side effects include:

- a. Decreased BP with symptoms of hypotension (e.g., dizziness or lightheadedness)
- b. Blood pressure or HR changes >20%

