- c. Pulse oximetry less than 94% that does not correct with several deep breaths.

Treatment of BP elevations > 20% of baseline will be treated with labetalol 5-15 mg IV incrementally until BP elevation <20% elevated. Treatment of symptomatic hypotension or BP reductions >20% will be treated with incremental ephedrine 5-20 mg, IV. Heart rate (HR) reductions or elevations > 20% of baseline will be treated with incremental glycopyrrolate 0.2 mg IV or propranolol 0.2 mg IV, respectively. Peripheral oxyhemoglobin desaturation (< 90) will be treated with supplemental oxygen, nasal cannula, face mask, or non-rebreathing mask depending upon the degree desaturation and the response to therapy.

Regardless of whether any treatment is required, subjects with significant side effects will be monitored more frequently (every 5 min for BP and HR; continuously for POX) until symptoms or signs resolve.

Serious adverse events: In addition to treatment, as described above, and timely reporting as required to the DSMC, IRB, and FDA, emergency treatment will be available within the CRU itself. As such, an ACLS-certified health care professional will be on site or within 5 minutes of the CRU during each treatment session, and a crash cart containing medicine and equipment for emergency resuscitation, and an automated external defibrillator will be located on-site.

Study Stopping Criteria: Should significant cardiorespiratory or other side effects occur during oxytocin administration, the IV infusion will be stopped and the subject treated as indicated in Treatment of Side Effects.

The study will be stopped if more than 2 individuals exhibit significant cardiorespiratory side effects or after any serious adverse event and future conduct of the study will be determined by recommendations from the DSMC, IRB, and FDA.

Outcome Measure(s)

Primary Outcome Measure

Name: Average verbal pain score (0-10) at one min intervals during the 5 min of skin heating

Type: Primary

Time Frame: For 180 minutes after the beginning of oxytocin infusion

Description: Pain scores are measured each minute during 5 min heating of the skin of the calf, with temperature of the probe determined in visit one to obtain a pain score at the end of this period of > 2.

Analytical Plan

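### The vital-sign schedule is worded for one infusion and has no anchor, so on any single clock at least one of the two infusions has no scheduled check strictly between its start and end

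*Combined protocol and SAP*

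**What the plan says.** All references are to the combined protocol and SAP.

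- **Regimen (Study Visit 2).** "Subjects will then receive two 30 min infusion of oxytocin, 17 µg", "with infusions separated by 30 min".
- **Routine monitoring (Safety and Monitoring, Assessment of Side Effects).** "Peripheral oxyhemoglobin saturation, BP and HR will be measured non-invasively" at these times: "before and 5, 10, 30, 60, 90 and 120 minutes after oxytocin infusion". Subjects are also asked to report sensations spontaneously, and they "will be queried at the same intervals as vital sign monitoring for any subjective sensations".
- **Significant cardiorespiratory effects (Treatment of Side Effects).** There are three criteria: a fall in blood pressure with symptoms, a change in blood pressure or heart rate of more than 20%, and oximetry below 94% that does not correct with deep breaths. Monitoring every 5 minutes, with continuous oximetry, applies to subjects who have had such an effect.
- **Stopping (Study Stopping Criteria).** "Should significant cardiorespiratory or other side effects occur during oxytocin administration, the IV infusion will be stopped". Separately, the study stops if more than 2 individuals show significant cardiorespiratory effects, or after any serious adverse event.
- **Contrast.** The pain tests in Study Visit 2 do have an anchor: "then at 3 hr after initiation of the first infusion".

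**The concern.** The monitoring sentence refers to a single infusion, but the regimen has two. It leaves three things open: which infusion, start or end, and whether the series is repeated. The schedule does not appear to have been carried over to the two-infusion design.

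This matters because the rule for stopping an infusion depends on finding an effect while the drug is running. Two of the three significant-effect criteria are established by measurement and need no symptom. If no measurement is scheduled within an infusion, an asymptomatic change that arises and resolves there may not be seen. One that persists may be found only when the infusion is already over. The symptom queries follow the same unanchored clock, so they do not fill the gap. The documents describe no other routine blood pressure, heart rate or oximetry check during an infusion.

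**Working it through.** There is no figure in the plan to reproduce. The check lists the scheduled times against the infusion windows.

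**Inputs**
- Offsets after the pre-infusion reading: 5, 10, 30, 60, 90 and 120 min (Assessment of Side Effects).
- Two infusions of 30 min each, separated by 30 min (Study Visit 2). Taking the separation as end of first to start of second, and the start of the first as time 0, infusion 1 runs 0-30 and infusion 2 runs 60-90.

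**Formula.** Check time = clock origin + offset. A check lies strictly inside an infusion if start < check time < end.

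| Clock origin | Check times (min) | Inside infusion 1 | Inside infusion 2 | On a boundary |
|---|---|---|---|---|
| Start of first (0) | 5, 10, 30, 60, 90, 120 | 2 (5, 10) | 0 | 30; 60 and 90 |
| End of first (30) | 35, 40, 60, 90, 120, 150 | 0 | 0 | 60 and 90 |
| Start of second (60) | 65, 70, 90, 120, 150, 180 | 0 | 2 (65, 70) | 90 |
| End of second (90) | 95, 100, 120, 150, 180, 210 | 0 | 0 | none |

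No single clock puts a check inside both infusions.

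**If the series repeats for each infusion**
- Restarted at each start: 5, 10, 30, 60, 65, 70, 90, 120, 150, 180. Two checks fall inside each infusion (5, 10 and 65, 70).
- Restarted at each end: 35, 40, 60, 90, 95, 100, 120, 150, 180, 210. None falls inside either infusion.

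**If the 30-min separation were start to start** (infusions at 0-30 and 30-60), the counts inside infusion 1 / infusion 2 are:
- start of first: 2 / 0
- end of first, which is also the start of second: 0 / 2
- end of second: 0 / 0

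Again no single clock covers both.

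**Sensitivity to exact timing.** On the start-of-first clock, if infusion 2 began at 58 min, the 60-min check would fall 60 - 58 = 2 min into it. If it began at 62 min, the 90-min check would fall 90 - 62 = 28 min into it. Small timing shifts can thus put one check just inside a boundary, leaving most of the infusion unmeasured.

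**The case against.** **The count depends on excluding boundaries.** On the start-of-first clock there are checks at 60 and 90 min, so the second infusion is not wholly unobserved, and a change persisting to 90 min would be seen. This stands. It narrows the gap to the interval between those two checks, but a change found at 90 min is found when there is no infusion left to stop.

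**A benign reading exists.** The close 5- and 10-minute offsets suit a clock that starts with the infusion, and staff may intend to restart it each time. That would cover both infusions. The text does not say so, however, and the reading has to be supplied by whoever runs the visit. The documents establish an ambiguity; they do not establish that an infusion will in fact go unmonitored.

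**Other safeguards operate.** Spontaneous symptom reporting works on any clock, and symptomatic hypotension is a listed criterion. Heat tests bring staff and subject together during the infusions, and closer monitoring follows any significant effect. All of this stands. What remains exposed is the asymptomatic change, especially a transient one.

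**Two stronger readings are tempting, and the documents do not support them.**
- A reader might infer that the stopping rules cannot work. The individual rule also covers symptomatic and other side effects. The study-level rule is not confined to events during infusion, and six post-baseline readings feed it on every single clock.
- A reader might infer that vital signs taken around the heat tests are confounded by pain and not comparable across the timing cohorts. On the start-of-first clock, the 30-, 60-, 90- and 120-min readings do fall at the end of a heat stimulus in the first 8 subjects. But that clock is not established. The 10-min cohort's own 5- and 10-min readings fall at the onset and end of its first stimulus. The documents give no figure for the effect of the heat stimulus on blood pressure or heart rate, and the Analytical Plan has no comparison of vital signs between cohorts.

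**Conclusion.** The point holds as a mismatch between the monitoring schedule and the regimen, and it should be corrected. On every single clock, at least one 30-minute infusion has no scheduled blood pressure, heart rate or oximetry check strictly between its start and end. On the two end-of-infusion clocks this is true of both infusions. A transient, asymptomatic change in blood pressure or heart rate of more than 20%, or a fall in oximetry, could be missed there or found too late to stop that infusion.

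The conclusion assumes nominal times, a strict reading of what counts as within the infusion, and a series run once. It does not hold if the series is meant to restart at the start of each infusion, which the text does not state. It has no bearing on the primary outcome or the PK/PD model, and the likelihood of such an event cannot be judged from the documents.

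**What to change.** Reconcile Assessment of Side Effects and Study Stopping Criteria with the two-infusion regimen in Study Visit 2. State the clock origin (which infusion, and its start or its end), and state how the series covers each of the two infusions, so that the rule for stopping an infusion can be applied during both. Carry the same wording into the visit worksheet and the symptom queries, which share the clock. The choice of times stays with the sponsor and the safety board.

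The cost is a sentence or two of protocol text and at most a few extra automated readings while the subject is already in the unit.

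### The jackknife tests only covariates already chosen on all 24 subjects, so its gain is not the stated estimate of utility in a future individual; the effect on which covariates are kept is modest

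*Combined protocol and SAP*

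**What the plan says.** All of this is in the Analytical Plan of the combined protocol and SAP, except the sample size.

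- Screening: "The influence of covariates (e.g., age, sex, weight) on model parameters will be analyzed by serial inclusion / exclusion". A covariate passes at p < 0.01, "if the decrease in -2 log likelihood exceeds 6.6".
- Entry to the second step: "Covariate effects deemed significant by likelihood ratio test will be validated using jackknife cross-validation".
- What each subset repeats: "The parameters of the model are re-estimated for each subset with and without the covariate being validated". Repeating the screen is not mentioned.
- Scoring: the inaccuracy "of the model with and without the covariate is measured in the excluded individual".
- Retention: a covariate enters the final model only "if the improvement in model accuracy in the N iterations is significantly greater than 0". The test, its level and its sidedness are not given. The reference to N iterations suggests one difference per subject, but this is not stated.
- Claimed property: "Jackknife cross-validation provides an estimate of the utility of the covariate to inform the pharmacodynamics in a future individual".
- Sample Size: "The projected sample size is 24 evaluable subjects with complete data sets".

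**The concern.** Leave-one-out prediction is honest about a new person only if nothing about the model was decided with that person's data. Here the parameters are re-estimated without the left-out subject, but the choice of covariate is not. A covariate reaches the jackknife because it fitted all 24 subjects well, including the one being predicted. The gain is therefore conditioned on a favourable draw and tends to be too high.

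Sex and age effects are the protocol's secondary objective, and the sample was raised to 24 to allow covariate assessment. The jackknife is the plan's only evidence that such a term would help predict someone new. The plan also says that it guards against very small covariate effects, which is where the optimism is greatest.

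**Working it through.** **Inputs from the documents.** N = 24 (Sample Size). Named candidates: age, sex and weight (Analytical Plan). Cut-off 6.6 on 1 df (Analytical Plan). Nine heat tests after the infusion starts: eight at 15 min intervals and one at 3 hr (Study Visit 2).

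**Assumptions, not in the documents.** Between-subject log SD 0.23-0.5. Residual SD 0 or 0.3. Independent noise candidates, numbering 1, 3 or 15 (15 = 3 covariates x 5 parameters). Retention by a one-sided 5% t test on the 24 per-subject differences. One log-normal parameter per subject stands in for the NONMEM fit.

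**1. The plan's cut-off.** The 0.99 quantile of chi-square on 1 df is 6.635, printed as 6.6 (exactly 6.6 gives p = 0.0102). The figure is reproduced.

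**2. The cut-off at N = 24, ideal normal regression.** The drop in -2 log likelihood is N x ln(1 + F/(N - 2)). So F = 22 x (exp(6.6/24) - 1) = 6.96, and p on (1, 22) df is 0.015. A true 1% would need 24 x ln(1 + 7.945/22) = 7.40. This is illustrative only.

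**3. How often noise reaches the jackknife.** Simulated: 1.4-1.6% per candidate, 4.6% for any of 3, 21% for any of 15. Arithmetic check at p = 0.015: 1 - 0.985^3 = 4.4% and 1 - 0.985^15 = 20.3%.

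**4. Apparent and true gain.** For each subject, the gain is the mean of |measured - predicted|/predicted without the covariate, minus the same with it. *Apparent* follows the plan. *New* applies the selected model to freshly simulated subjects. *Nested* repeats the screen in every subset, uses the best candidate that passes there, and predicts without a covariate if none does. Results are in points (x 100), among trials where a covariate passed 6.6, with residual SD 0.3:

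| Setting | Apparent | New | Nested | Retained, plan | Retained, nested |
|---|---|---|---|---|---|
| Noise, 1 candidate, SD 0.3 | +2.77 | -3.66 | +0.25 | 8.3% | 4.9% |
| Noise, 3 candidates, SD 0.3 | +2.86 | -3.79 | +0.21 | 8.4% | 5.7% |
| Noise, 15 candidates, SD 0.3 | +2.78 | -3.61 | -0.39 | 6.1% | 3.2% |
| Noise, 3 candidates, SD 0.5 | +5.84 | -8.05 | +0.10 | 7.7% | 5.0% |
| Real, slope 0.2 per SD, SD 0.3 | +5.72 | +4.07 | +4.52 | 25.3% | 23.8% |
| Real, slope 0.4 per SD, SD 0.3 | +16.07 | +16.46 | +15.89 | 69.3% | 69.3% |

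Baseline inaccuracy is about 0.37 at SD 0.3 and 0.53 at SD 0.5 in the noise rows.

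With the subject parameter known exactly, 15 noise candidates and log SD 0.23-0.45 (CV about 23-47%), the apparent gain is +2.5 to +5.4 against a true -3.0 to -7.0. Nested it is +0.2 to +0.4. Retention given a pass is about 12-15% under the plan and 7-8% nested.

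Across settings the apparent gain is positive in 96-100% of screened noise covariates, against 18-21% of unscreened ones.

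**5. Real sex effects, apparent against true.** For a 20% effect: +3.7 against +1.2 at CV 23%, and +6.9 against -2.0 at CV 47%. For a 40% effect, the range that the Sample Size section targets: +5.8 against +4.7 at CV 23%, and +7.7 against +1.4 at CV 47%.

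**6. Trial-level false retention, 15 noise candidates.**
- With residual noise: 0.2063 x 0.061 = 1.3%; nested, 0.2063 x 0.032 = 0.7%.
- Parameter known exactly: 0.20 x 0.12 = 2.4% to 0.21 x 0.15 = 3.2%; nested, 0.20 x 0.07 = 1.4% to 0.21 x 0.08 = 1.7%.

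The reduction from nesting is 32-48% across settings. With only 3 candidates, false retention is 0.046 x 0.084 = 0.4%.

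**7. Dependence on the unit of the test.** If individual ratings were pooled as independent, 72-76% (one-sided) or 56-66% (two-sided) of screened noise covariates would pass the second step.

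**The case against.** The strongest reply is that the plan acts on significance, not on the sign of the gain. The second step can only remove covariates, and a per-subject test removes about 85% or more of screened noise terms at one-sided 5% in most settings. For a true 40% sex effect at CV 23%, overall retention is 33.5% as planned and 33.2% with nesting. The plan nowhere promises to report the size of the gain. All of this stands, and it keeps the point to an analysis correction.

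Four stronger readings are not supported:

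- A reader might infer that noise covariates will nearly always be kept. The figure of 96-100% concerns only the sign of the gain after the screen.
- A reader might infer that every selected covariate's gain is inflated. At slope 0.4 it was 16.07 against 16.46, so it was not.
- A reader might infer that 6.6 is an error or that 7.4 should replace it. The former is the correct asymptotic value. The latter assumes ordinary regression on exactly known parameters, not the planned conditional estimation on repeated ratings.
- A reader might infer that nesting recovers the value of the named covariate in a new person. It does not: nested noise averages about 0 while the true change is negative, because nesting scores the selection procedure.

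The number of covariate-parameter pairs is also assumed; if C90 is derived from C50 and gamma, it would be 12, not 15.

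The reply does not rescue the stated property. The plan presents the jackknife as an estimate of future utility, and with selection outside the loop it is not one. The protection also depends on a test that the plan leaves unspecified.

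**Conclusion.** The concern holds in limited form. For a covariate selected on all 24 subjects, the jackknife gain does not estimate its utility in a future individual. It is optimistic for noise and weak effects: about +2.5 to +5.5 points apparent against about -3 to -7 true for noise, at CV 23-47%. It is nearly unbiased when the effect is large relative to between-subject spread. At the 40% effect that the plan targets, the bias is small at CV 23% and substantial at CV 47%; the documents give no CV, so its size in this trial is unknown.

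The consequence for retention is modest: roughly 1.3-3% trial-level false retention with 15 candidates, and about 40% less with nesting, provided that the test is per subject. The percentages come from a simplified subject-level model and are approximate. The direction was the same in every noise setting tried. What needs correcting is mainly the claim attached to the jackknife and the procedure behind it.

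**What to change.** Amend the Analytical Plan as follows.

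1. In each leave-one-out subset, repeat the likelihood-ratio screen as well as the parameter estimation. Where the covariate is not selected in that subset, predict the left-out subject without it. State in advance what is done if a different covariate is selected there.
2. Apply the improvement test to the N per-subject differences, and state the test, level and sidedness.
3. Describe the result as the predictive performance of the selection procedure, not of the named covariate.

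Optional and secondary: because 6.6 is likely somewhat liberal at N = 24 (p about 0.015 in the ideal case), the cut-off may be set by permuting covariates across subjects. Do not hard-code 7.4.

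Cost: one nested pass over 12-15 pairs is 24 x 12 = 288 to 24 x 15 = 360 covariate fits; further inclusion or exclusion steps add to this. Permutation costs more: 200 permutations x 12 pairs is 2,400 fits, and 200 is too few to fix a 1% cut-off precisely. Nesting loses little sensitivity: given a pass, retention of a strong real effect fell from 49% to 47% in one setting and stayed at 69.3% in another. Design, dosing and recruitment are unchanged.
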